4.3. Outcome Definitions

4.3.1. Pregnancy Outcomes of Interest

The following pregnancy outcomes will be collected by the registry:

- Spontaneous miscarriage: fetal death or expulsion of products of conception prior to 20 weeks' (<20 weeks) gestation
- Live birth: the birth of a living fetus at 20 weeks' gestation or greater (\geq 20 weeks), or, if gestational age is unknown, a fetus weighing 500 g or more (\geq 500 g)
- Stillbirth: a fetal death occurring at 20 weeks' gestation or greater (≥20 weeks), or, if gestational age is unknown, a fetus weighing 500 g or more (≥500 g)
- Elective termination: voluntary interruption of pregnancy, including pregnancy termination that occurs electively, to preserve maternal health, or due to fetal abnormalities
- Preterm birth: an infant born at gestational age less than 37 weeks (<37 weeks)
- Neonatal death: an infant who after live birth expired within the first 28 days (≤28 days) of life
- Ectopic pregnancy: implantation of a conception outside of the uterus
- Molar pregnancy: a conception that results in a gestational trophoblastic tumor
- Small for gestational age (SGA): defined as an infant whose birth weight is less than the 10th percentile for the gestational age. It is based on data derived from an appropriate reference population. The registry will utilize the sex specific international growth reference standards from the International Fetal and Newborn Growth Consortium for the 21st Century (INTERGROWTH-21st) for those born at ≥33 weeks gestational age (Villar, 2014). The INTERGROWTH-21st standards are the latest available global reference standards, representing contemporary information from an international, multiethnic, diverse population and have been specifically developed for modern research. As the INTERGROWTH-21st standards are valid for infants born between 33^{0/7} and 42^{6/7} weeks gestation, SGA will be additionally classified using the reference standard endorsed by the American Congress of Obstetricians and Gynecologists (ACOG) which is applicable for the entire range of gestational age (Alexander, 1996).

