4.6.3.2. Information Collected at Pregnancy Outcome

Maternal SLE Disease Severity and Health Conditions

- Measurement of SLE disease activity by PGA If available:
 - Autoantibody testing results (anti-ds DNA, anti-cardiolipin antibodies, lupus anticoagulant, anti-Ro, anti-La)
 - Complement levels (C3/C4)
- Updated assessment of proteinuria, serum and urine creatinine
- Concurrent medical conditions (update on changes during pregnancy)
- Concomitant medications

Maternal Belimumab or other SLE treatment Exposure and Other Exposures

- Belimumab or SLE treatment course with dates of treatment. Dose and route of administration will be collected for belimumab exposed participants only.
- Tobacco, alcohol, and recreational drug use

Pregnancy outcome

- Date of pregnancy outcome
- Pregnancy type (singleton, twin, triplet, other)

- Subsequent prenatal imaging and aneuploidy screening/testing performed and findings including the identification of birth defects
- Pregnancy outcome (e.g., live birth, stillbirth, neonatal death, spontaneous miscarriage, elective termination, ectopic pregnancy, molar pregnancy)

Fetal Outcome

- Fetal/infant characteristics (e.g., gender, birth weight, length, head circumference)
- Birth defect(s) and assessment of potential contributing factors
- For a fetal loss (spontaneous miscarriage, stillbirth, ectopic pregnancy, molar pregnancy), factors that may have had an impact on the fetal loss and attribution
- Serious and/or clinically significant infections in the infant
- Breastfeeding status (see Glossary)

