4.8.3.1. Population-Based Birth Defects Surveillance Programs

The Centers for Disease Control and Prevention (CDC) Metropolitan Atlanta Congenital Defects Program (MACDP) classification system will be used as the primary comparator data for defining and coding of birth defects for all registry sites. For the occurrence of birth defects, CDC MACDP data will be used for all sites as it is widely used as a comparator in pregnancy registries. The European Surveillance of Congenital Anomalies (EUROCAT) data will be used as a secondary comparison for European sites.

The primary objectives of CDC MACDP are to regularly and systematically monitor births of malformed infants to monitor changes in incidence or other unusual patterns and to develop a case registry for use in epidemiological studies. CDC MACDP actively searches for birth defects among the 50,000 annual births to residents of metropolitan Atlanta's 5 counties and abstracts medical records at all Atlanta obstetric hospitals, pediatric referral hospitals, genetics laboratories, and vital records [Correa-Villasenor, 2003]. CDC MACDP data have been used as a comparator cohort in examinations of birth defects for other pregnancy registries (acyclovir, sumatriptan, lamotrigine, and zidovudine) [Honein 1999]. The most recent CDC MACDP 5-year prevalence of 2.78% (6,945 cases with birth defects/249,999 live births) from 1999 to 2003 is deemed the most appropriate comparator birth defect data [Correa, 2007], due to lack of adequate birth defect data for the offspring of SLE mothers.

The total prevalence of birth defects overall in EUROCAT (including fetal deaths and pregnancy terminations) from 2004-2008 was 2.33% (http://www.eurocat-network.eu/). EUROCAT is a European network of population-based registries, including 43 registries in 20 countries, and it covers 29% of the European population. It started in 1979 and includes 1.5 million births per year in Europe. Its primary objectives are to provide essential epidemiological information on congenital anomalies and to act as an information and resource center to individuals and public health professionals.

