4.8.4.2. Birth Defects

The prevalence of birth defects reported to the registry will be calculated as the percentage of birth defects from the total number of live births. The differences between the observed registry birth defect rates and these comparators will be estimated along with 95% confidence intervals. Fetal losses with reported birth defects occurring at or after 20 gestation weeks will be included in the numerator of the estimate of risk for birth defects to increase sensitivity and to allow comparison post-outcome with the CDC MACDP and EUROCAT. The analysis will also be conducted including fetal losses with reported birth defects occurring at less than 20 gestational weeks in the calculation of risk. It is possible that the background birth defect rate in the overall population may be different from the birth defect rate in SLE patients. Accordingly, additional analyses using different appropriate external SLE comparator cohorts will also be performed.

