9. GLOSSARY

Term	Registry Definition
Birth defect	The registry defines a birth defect as any major structural or chromosomal defect or 2 or more conditional defects in live-born infants, stillbirths, or fetal losses of any gestational age (including outcomes prior to 20 weeks' gestation or weighing <500 g). This definition is consistent with but not restricted to the CDC MACDP definition.
Breastfeeding	Providing mother's own milk for infant nutrition
Conditional defect	The registry defines a conditional defect as a condition which appears in the MACDP Exclusion List.
Corrected EDD	Estimated date of delivery obtained by prenatal test (e.g., ultrasound) when the LMP is unknown or deemed to be unreliable for estimating gestational age.
Date of conception	Calculated as the most reliable EDD minus 38 weeks.
Eclampsia	A life-threatening condition of pregnancy following pre-eclampsia characterized by seizures that are unrelated to a preexisting brain condition.
Ectopic pregnancy	Implantation of a conception outside of the uterus.
Elective termination	Voluntary interruption of pregnancy prior to natural outcome. Includes pregnancy termination that occurs electively, to preserve maternal health, or due to fetal abnormalities. Terminology may include elective abortion, therapeutic abortion, artificial abortion and induced abortion.
End of pregnancy	Defined as live birth, fetal loss (i.e. spontaneous miscarriage, stillbirth, ectopic pregnancy, molar pregnancy), etc.
Estimated due date (EDD)	The calendar date upon which it is estimated that the baby will be born, calculated as the LMP + 40 weeks.
European Surveillance of Congenital Anomalies (EUROCAT)	A network of population-based registries for the epidemiologic surveillance of congenital anomalies that began in 1979. Currently it includes 43 registries in 20 countries and covers 29% of the European birth population. It is a resource for the development of uniform methods and approaches to birth defect surveillance.
Fetal loss	Defined as spontaneous miscarriage, stillbirth, ectopic pregnancy, molar pregnancy

Term	Registry Definition
Gestational diabetes	Any degree of glucose intolerance with onset or first recognition during pregnancy.
Gestational hypertension	The development of high blood pressure after 20 weeks of pregnancy; this condition is not associated with proteinuria or other signs of pre-eclampsia and may also be known as pregnancy-induced hypertension.

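### The birth-defect numerator leaves out elective terminations, while the EUROCAT figure it is meant to be compared with includes them

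*Protocol*

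**What the plan says.** Protocol Section 4.8.4.2 calculates prevalence as the "percentage of birth defects from the total number of live births". It then widens the numerator: "Fetal losses with reported birth defects occurring at or after 20 gestation weeks will be included in the numerator of the estimate of risk". One stated reason is "to allow comparison post-outcome with the CDC MACDP and EUROCAT". A second calculation goes further: "The analysis will also be conducted including fetal losses with reported birth defects occurring at less than 20 gestational weeks". Section 4.8.1 gives the same two rules.

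The glossary entry for fetal loss reads: "Defined as spontaneous miscarriage, stillbirth, ectopic pregnancy, molar pregnancy". Section 4.6.3.2 lists the same four outcomes when it describes data collection. Section 4.3.1 defines elective termination separately, and that definition includes "pregnancy termination that occurs electively, to preserve maternal health, or due to fetal abnormalities".

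Section 4.8.3.1 makes MACDP the primary comparator for all sites (2.78%, from 6,945 cases in 249,999 live births) and EUROCAT a secondary comparison for European sites. On EUROCAT it says: "The total prevalence of birth defects overall in EUROCAT (including fetal deaths and pregnancy terminations) from 2004-2008 was 2.33" percent.

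**The concern.** The two sides of the EUROCAT difference count different things. EUROCAT's figure includes affected pregnancies that were terminated. The registry's numerator, read with the registry's own definitions, does not.

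The primary population makes this relevant. Pure prospective cases have had no prenatal testing before enrollment (Sections 4.6.8.1 and 4.8.2), so any prenatal diagnosis, and any termination that follows it, falls within follow-up. The registry records screening and imaging findings and includes chromosomal defects (Sections 4.3.2 and 4.6.3). It would therefore collect such a case and then leave it out of the rate.

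At stake is the accuracy of one of the two planned external comparisons for the primary endpoint. The error runs in one direction, towards a lower apparent risk, and a larger enrollment would not remove it.

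**Working it through.** **1. The plan's own figure.** Section 5 assumes 350 live births and an observed prevalence of 2.78%. The expected count is 350 × 0.0278 = 9.73, and the exact (Clopper-Pearson) interval at that count is 1.325% to 5.093%. This matches the stated 1.32% to 5.09%. The width is 5.09 − 1.32 = 3.77 percentage points. Nothing below disputes this figure.

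**2. Which outcomes enter the rate.**

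| Outcome with a reported defect | Main estimate | Additional analysis | EUROCAT 2.33% (as Section 4.8.3.1 describes it) |
|---|---|---|---|
| Live birth | yes | yes | yes |
| Fetal loss, 20 weeks or later | yes | yes | fetal deaths included |
| Fetal loss, before 20 weeks | no | yes | fetal deaths included; gestational limit not stated |
| Elective termination, 20 weeks or later | not named | not named | terminations included |
| Elective termination, before 20 weeks | not named | not named | terminations included; gestational limit not stated |

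**3. Size of the mismatch.** Let s be the share of all defect cases that end in elective termination. The documents give no value, so s = 5% to 30% is an assumption. If the true total prevalence equals EUROCAT's 2.33%:

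- registry prevalence as calculated = 2.33% × (1 − s)
- spurious difference from EUROCAT = −2.33% × s
- cases left out at 350 live births = 350 × 0.0233 × s = 8.16 × s

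| s (assumed) | Prevalence shown | Difference (points) | Cases left out, n = 350 |
|---|---|---|---|
| 5% | 2.21% | −0.12 | 0.4 |
| 10% | 2.10% | −0.23 | 0.8 |
| 20% | 1.86% | −0.47 | 1.6 |
| 30% | 1.63% | −0.70 | 2.4 |

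The difference in points does not depend on the number of live births, so it is the same at 311, 350 or 380.

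**4. Effect of one case.** At 350 live births one omitted case is 1/350 = 0.29 points. The EUROCAT comparison is for European sites, whose number of live births is not given, so the effect per case there is larger. If half of the 350 were European (an illustration only), it would be 1/175 = 0.57 points.

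**The case against.** **EUROCAT is only the secondary comparator.** This stands and limits the point. A reader might infer the same mismatch against MACDP, but the protocol does not say whether MACDP's 2.78% counts terminations. No bias against MACDP is shown. Adding terminations to the main estimate without checking could create a mismatch there.

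**Section 4.3.2 says data from aborted fetuses under 20 weeks will be included when available.** This leaves early terminations ambiguous, because the glossary uses abortion terms for both miscarriage and elective termination. It does not repair the rule. The phrase is tied to sensitivity of monitoring, says nothing of terminations at 20 weeks or later, and is not carried into Sections 4.8.1 or 4.8.4.2. Even on the generous reading, early terminations would enter only the additional analysis.

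**The effect is small against the planned precision.** True: 0.12 to 0.70 points against an interval 3.77 points wide. But the interval reflects chance, and this is a systematic shift.

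**A reader might infer that a real increase in risk could be masked.** The documents do not support that without qualification. The registry is descriptive, terminations are reported as an outcome with a confidence interval (Section 4.8.4.1), and Section 7.11 provides for individual and cumulative review of all reported defects regardless of this numerator. Counting two or more conditional defects as a case, which Section 4.3.2 says MACDP does not do, pushes the registry rate upward, so the net direction against MACDP is not known.

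**A reader might infer from the trial data in Section 1.1 that such terminations are common.** There, 44 known belimumab outcomes less the 34 left after excluding elective terminations gives 10. No reasons are stated, and these women had been instructed to use contraception and were withdrawn from treatment on a positive test. The figure does not show how often a defect leads to termination.

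**Conclusion.** The point holds for the EUROCAT comparison. As written, the estimation rules omit elective terminations with defects, the EUROCAT figure includes terminations, and the rule therefore fails one of its stated purposes. The resulting bias in the registry-minus-EUROCAT difference is downward. Its size is about −0.12 to −0.70 percentage points, on the assumptions that 5% to 30% of defect cases end in termination, that all of these are left out, and that the true total prevalence is 2.33%. The direction follows from the definitions; the size rests on an assumed share. Whether the primary MACDP comparison has the same fault cannot be settled from the protocol.

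**What to change.** - In Sections 4.8.1 and 4.8.4.2, count elective terminations with reported defects, at any gestational age, in the numerator of the estimate compared with EUROCAT total prevalence. Alternatively, use a EUROCAT figure that excludes terminations.
- For MACDP, first confirm from the source whether the 2.78% counts terminations. Match the main numerator to it, and report the estimate both with and without terminations.
- In Section 4.3.2, say whether the reference to aborted fetuses means spontaneous losses, induced terminations or both. Make the case definition there and in the glossary agree with the estimation rules.

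Outcome type and birth defects are already recorded at pregnancy outcome (Section 4.6.3.2), so no new data are needed. The cost is a wording change and one additional reported estimate.

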4.8.4.3. Serious and/or Clinically Significant Infections in Infants

The frequency and proportion of infections in infants (as defined in Section 4.3.3) during the infant's first year of life and 95% CI will be calculated, with the number of live births

as the denominator. These frequencies and proportions will be tabulated by timing and level of exposure to belimumab, breastfeeding status and length of infant follow-up.

For all outcomes of interest, comparisons between the registry data and data from appropriate external comparison cohorts will be considered, if available.

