2.2. Endpoints

Primary Endpoint:

• Birth defects

Secondary Endpoints:

Other pregnancy outcomes

• Spontaneous miscarriage

- Live birth (preterm birth and small for gestational age (SGA))
- Stillbirth
- Elective termination

Infant outcomes through age 1 year

• Serious and/or clinically significant infections

These endpoints are defined in Section 4.3 of the protocol.

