4.3.3. Serious and/or Clinically Significant Infections in Infants

All infections that meet the serious adverse event criteria as per Section 7.4 will be reported for infants through 12 months of age. Certain non-serious events will additionally be reported as clinically significant and will include:

• Infants from birth through 6 months of age: infections requiring treatment

• Infants from birth through 3 months of age: fevers of unknown origin or of known infectious etiology

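### The first-year infant infection proportion pools components that stop at 3, 6 and 12 months and is not split by seriousness, so it is not a first-year risk of any one event and dilutes a rise in serious infections

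*Protocol*

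**What the plan says.** Protocol section 2.2 lists a single infection endpoint, serious and/or clinically significant infections, under "Infant outcomes through age 1 year".

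Section 4.3.3 builds it from three components:

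- Serious: "All infections that meet the serious adverse event criteria as per Section 7.4 will be reported for infants through 12 months of age".
- The non-serious part is introduced with "Certain non-serious events will additionally be reported as clinically significant and will include", followed by two items.
- First item: "Infants from birth through 6 months of age: infections requiring treatment".
- Second item: "Infants from birth through 3 months of age: fevers of unknown origin or of known infectious etiology".

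Section 4.8.4.3 turns this into a summary measure: "The frequency and proportion of infections in infants (as defined in Section 4.3.3) during the" and then "infant's first year of life and 95% CI will be calculated, with the number of live births" as the denominator. It adds: "These frequencies and proportions will be tabulated by timing and level of exposure to belimumab, breastfeeding status and length of infant follow-up". It closes by saying that comparisons with suitable external cohorts will be considered for all outcomes of interest, if such data exist. Section 4.8.4 bases comparisons with external SLE cohorts on the observed frequency and the lower 95% confidence limit.

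**The concern.** Section 4.8.4.3 sets the numerator, denominator, period and breakdowns of the measure, so a programmer following it would produce one proportion labelled as first-year. In that proportion, an infant with a treated non-serious infection at 5 months is an event, and an infant with the same infection at 7 months is not. A single fever at 2 months counts the same as a hospitalised infection.

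Two things are at stake. The number does not estimate the first-year risk of anything a reader would recognise, so an external first-year rate is not a valid yardstick for it unless that rate uses the same 12/6/3-month mixture. Also, a rise in serious infections is diluted by events that are unchanged. Section 1.1 reports reduced B cells and IgM in infant monkeys exposed in utero, and infection is the only infant outcome named among the secondary endpoints, so the measure should be able to show such a rise.

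**Working it through.** **Windows side by side**

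| Component (section 4.3.3) | Counted from birth to | Label in sections 2.2 and 4.8.4.3 |
|---|---|---|
| Infections meeting SAE criteria | 12 months | first year |
| Non-serious infections requiring treatment | 6 months | first year |
| Fevers, unknown origin or infectious | 3 months | first year |

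Only the first row matches the label. Tabulating by length of follow-up does not help: an infant observed for all 12 months still contributes to three different windows, because the windows differ by definition and not through dropout.

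**Inputs for the dilution calculation**

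- Live births: n = 350, from protocol section 5. The same section gives a range of 311 to 380, which reproduces: 500 × 0.83 × 0.75 = 311.25 and 500 × 0.95 × 0.80 = 380.
- The protocol's only precision figure is for birth defects: an exact 95% CI of (1.32%, 5.09%) at 2.78%. The Clopper-Pearson formula with x = 0.0278 × 350 = 9.73 gives (1.33%, 5.09%), which agrees within rounding. No figure is given for infections.
- All infection rates are assumptions. Serious risk s rises from 4% to 8%. Non-serious risk q (a treated infection or fever within its window) is unchanged, is independent of serious infection, and ranges from 2% to 50%.

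**Formulas**

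- Pooled risk = 1 − (1 − s)(1 − q). For q = 20%: 1 − 0.96 × 0.80 = 23.2%, rising to 1 − 0.92 × 0.80 = 26.4%.
- Chance of a signal: find the smallest count out of 350 whose exact lower 95% limit exceeds the reference risk, then take the binomial probability of reaching that count at the raised risk. For serious infections alone the threshold is 23 events, and the probability at 8% is 86%.

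**Results, n = 350**

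| Measure | Reference → raised | Rise (points) | Risk ratio | Chance that lower limit exceeds reference |
|---|---|---|---|---|
| Serious alone | 4.0% → 8.0% | 4.0 | 2.00 | 86% |
| Pooled, q = 2% | 5.9% → 9.8% | 3.9 | 1.66 | 76% |
| Pooled, q = 5% | 8.8% → 12.6% | 3.8 | 1.43 | 59% |
| Pooled, q = 10% | 13.6% → 17.2% | 3.6 | 1.26 | 48% |
| Pooled, q = 20% | 23.2% → 26.4% | 3.2 | 1.14 | 27% |
| Pooled, q = 35% | 37.6% → 40.2% | 2.6 | 1.07 | 17% |
| Pooled, q = 50% | 52.0% → 54.0% | 2.0 | 1.04 | 11% |

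The absolute rise retained is 4(1 − q) points. At q = 20%, 35% and 50% that is 80%, 65% and 50% of the true 4-point rise. The rest of the loss comes from the larger variance at a higher base rate: the standard error is about 1.0 to 1.5 points for serious infections alone and about 2.3 to 2.7 points for the pooled figure at q = 20% to 50%.

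**Sensitivity.** With n from 311 to 380 and a doubling from a baseline s of 3% to 8%, the chance is 69% to nearly 100% for serious infections alone. Pooled, it is 28% to 99% at q = 2% to 10%, and 6% to 78% at q = 20% to 60%.

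**The case against.** The case on the other side has weight in several places.

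- The windows are stated openly in section 4.3.3, and section 4.8.4.3 cross-refers to them. Different windows are not an error in themselves. Section 1.1 reports recovery of infant monkey B cells by 3 months and IgM by 6 months. The protocol does not make the link, but counting milder events only over such periods would be coherent. This stands: the fault lies in the pooled first-year label, not in the windows.
- Serious infections are not seen only through this proportion. Section 7.4 sends every SAE to the sponsor within 1 business day, section 7.10 has the advisory committee review data at least annually, and section 7.11 asks it to develop infection signal criteria. This also stands, but none of it supplies a proportion with a confidence interval. The signal criteria are not yet defined and refer to the same combined category.
- The registry is descriptive and names no external infection rate, and section 4.8.3.2 already warns that differing classifications complicate comparison. The signal probabilities above therefore illustrate information lost; they are not the power of a planned test.
- Table layout usually belongs to the analysis plan. That would answer a complaint about missing detail, but section 4.8.4.3 itself fixes the measure and its breakdowns. Nothing forbids adding a split; nothing provides for one either.

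A reader might infer that a serious-infection signal is bound to be swamped, or that most of a real rise would be hidden. The documents support neither. They give no non-serious rate, so the degree of dilution is unknown, and in the scenarios above at least half of the absolute rise survives.

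**Conclusion.** The point holds as a badly fixed summary measure for a named secondary safety endpoint. As written, the first-year proportion is not the first-year risk of any one kind of event, should not be compared with an external first-year rate, and dilutes a change in serious infections.

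That dilution occurs follows from the definition, given any non-serious events at a rate that does not itself change. Its size is conditional. For serious infections doubling from 4% to 8% in 350 infants, independent of non-serious events, the chance that the lower limit clears the reference falls from 86% to between 76% and 48% if non-serious events affect 2% to 10% of infants, and to between 27% and 11% if they affect 20% to 50%. If non-serious events are rare, the pooled figure would often still show the rise. Individual SAE review remains as a separate safeguard.

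**What to change.** In protocol section 4.8.4.3:

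- Report serious infections from birth through 12 months as their own proportion of live births with a 95% CI.
- Report non-serious treated infections through 6 months, and fevers through 3 months, as separate proportions, each labelled with its window.
- If a pooled figure is kept, do not call it a first-year rate and do not compare it with external first-year rates.

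Align the endpoint wording in section 2.2 and carry the split into the analysis plan.

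The cost is wording and two extra table rows, since section 4.3.3 already defines the components and section 4.6.4 already collects infant infection and fever histories. The downside is three infection proportions to interpret in place of one.

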4.2. Study Design

This global pregnancy registry will be a multi-center, prospective cohort study with voluntary participant registration following informed consent by the pregnant woman for her participation and assent for participation of her infant. The registry will be strictly observational; the schedule of office visits and all treatment regimens will be determined by the treating HCP. The registry will collect data that are routinely documented in the participant's medical record in the course of usual care, with the possible exception of the Physician Global Assessment (PGA) of SLE disease activity (Appendix 1) and the SLICC/ACR Damage Index (SDI; Appendix 2). The PGA is a simple, concise, global index of disease activity [Petri, 1992] that will be completed at registration (including a pre-conception assessment), towards the end of 2nd trimester and at pregnancy outcome for registry participants with SLE. SLE disease activity is often assessed in usual clinical care and collection of this information will be integral to evaluating disease severity during the pre-conception period through the end of pregnancy. The SDI records irreversible organ system damage occurring in participants with SLE regardless of etiology. Damage may be attributed to active SLE disease, concomitant medication or intercurrent illness [Gladman, 1996].

Data will be collected at registration (early in pregnancy to include pre-conception SLE disease severity), at the end of the second trimester (approximately 26 weeks' gestation), and at pregnancy outcome (delivery or early termination). For live births, infant outcomes at the time of birth will be reported. Infants will be followed up for outcomes at 4 and 12 months of age. Targeted follow-up will also take place to gather additional information, if required to assist data interpretation on events and outcomes of interest. This registry is intended to enroll participants with SLE.

Retrospective reports of pregnancy are those in which the pregnancy ended (live birth, fetal loss, etc) before enrollment or at the time of first contact with the registry. All

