4.6.8.3. Lost to Follow-Up

For a prospective report or pregnancy where follow-up information on the pregnancy outcome, from a HCP, is never obtained, unavailable, and/or where the indication of a birth defect is designated as unknown, the pregnancy will be considered lost to follow-up. Cases lost to follow-up prior to pregnancy outcome will be tallied in the registry reports but not included in the primary study population. For infants, if pediatric follow-up information, from a HCP, is never obtained, unavailable, and/or where infant status is designated as unknown, the infant will be considered lost to follow-up. Any cases with infant outcome will be analyzed according to the length of infant follow up.

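### First-year infant infections are divided by all live births, so infants whose follow-up is missing or cut short, with no infection recorded, count as infection-free and pull the overall proportion and its lower 95% limit down

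*Protocol*

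**What the plan says.** Section 4.8.4.3 gives the rule for the only infant endpoint among the secondary endpoints: "first year of life and 95% CI will be calculated, with the number of live births" as the denominator. Its next sentence tabulates the same figures by timing and level of exposure and by "breastfeeding status and length of infant follow-up".

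Section 4.6.8.3 covers loss at two stages.

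- For pregnancies: "Cases lost to follow-up prior to pregnancy outcome will be tallied in the registry reports but not included in the primary study population".
- For infants, loss means that no pediatric information came from a health care provider, or, as the text continues, "where infant status is designated as unknown, the infant will be considered lost to follow-up". No exclusion follows for them, only this: "Any cases with infant outcome will be analyzed according to the length of infant follow up".

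The observation windows are in Section 4.3.3. Serious infections "will be reported for infants through 12 months of age". Non-serious infections needing treatment count to 6 months, and fevers to 3 months.

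The contacts are in Section 4.2: "Infants will be followed up for outcomes at 4 and 12 months of age". Section 4.6.3.2 adds one earlier capture point, since the pregnancy-outcome form also asks for "Serious and/or clinically significant infections in the infant".

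**The concern.** A proportion over a fixed window needs a denominator of infants whose status over that window is known. Live births is a wider group. An infant who leaves the registry after birth stays in the denominator for the whole year but can add an event only if the infection was reported before contact ended. Unknown status is thus read as no infection.

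Partial follow-up has the same effect. An infant last seen at 4 months has completed the 3-month fever window but not the 6- or 12-month windows, yet counts fully towards all of them.

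The protocol respects this principle elsewhere. Section 4.8.4.1 limits the miscarriage denominator to pregnancies enrolled before week 20, and Section 4.6.8.3 removes pregnancies of unknown outcome. Infants of unknown infection status get no such treatment.

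At stake is the direction of the error on a safety endpoint. Section 1.1 reports reduced B cells and IgM in infant monkeys (recovered by 3 and 6 months respectively), so infection in early life is the natural outcome to watch. Section 4.8.4 compares the registry with external SLE cohorts on the observed frequency and its lower 95% limit. Both are lowered by the live-birth denominator, so an excess is harder to see.

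**Working it through.** **The plan's own figures (Section 5).** Live births = 500 × live-birth share × (1 − loss).

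- Lower: 500 × 0.83 × 0.75 = 311.25, stated as 311.
- Upper: 500 × 0.95 × 0.80 = 380, stated as 380.
- Exact (Clopper-Pearson) 95% CI with 350 live births and 0.0278 × 350 = 9.73 events: 1.325% to 5.093%, stated as 1.32% to 5.09%.

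These reproduce. They also show that the 20-25% loss has already been spent in reaching the 311 to 380 live births. The protocol states neither a loss rate for infants after birth nor an expected infection risk.

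**Direction.** Let L be the share of live-born infants lost, p_F and p_L the risks in followed and lost infants, and q the share of lost infants' infections recorded before loss.

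- True risk among all live births: p_F(1 − L) + p_L·L
- Reported on live births: p_F(1 − L) + q·p_L·L
- Shortfall: (1 − q)·p_L·L

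The shortfall is never negative, whatever p_F and p_L are. If p_F = p_L = p and q = 0, the reported figure is p(1 − L), and the relative understatement is L.

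**Size, by illustration.** Assumptions, none from the protocol except the 350: 350 live births (the Section 5 scenario), p = 10% in lost and followed infants alike, q = 0. Followed infants and events are rounded to whole numbers, and intervals are exact 95%.

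| Infant loss | Events | On live births | On followed infants |
|---|---|---|---|
| 5% | 33 | 33/350 = 9.4% (6.6 to 13.0) | 33/332 = 9.9% (6.9 to 13.7) |
| 10% | 32 | 32/350 = 9.1% (6.3 to 12.7) | 32/315 = 10.2% (7.1 to 14.0) |
| 20% | 28 | 28/350 = 8.0% (5.4 to 11.4) | 28/280 = 10.0% (6.7 to 14.1) |
| 25% | 26 | 26/350 = 7.4% (4.9 to 10.7) | 26/262 = 9.9% (6.6 to 14.2) |
| 40% | 21 | 21/350 = 6.0% (3.8 to 9.0) | 21/210 = 10.0% (6.3 to 14.9) |

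At 20% loss the interval on live births is also narrower than the data support: 11.4 − 5.4 = 6.0 points against 14.1 − 6.7 = 7.4, because infants who were not observed are counted as observed. In this table the live-birth interval misses the assumed 10% only at 40% loss.

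**Early capture.** With q = 0.5:

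- 20% loss: 0.10 × 0.80 + 0.5 × 0.10 × 0.20 = 9.0%
- 25% loss: 0.10 × 0.75 + 0.5 × 0.10 × 0.25 = 8.75%

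**The case against.** The best defence is the tabulation by length of follow-up, promised in Section 4.8.4.3 and echoed in Section 4.6.8.3. If each follow-up stratum had its own denominator, the 12-month row would be close to the figure one wants for serious infections. This has real weight. But the protocol gives no stratum-specific denominator, the tabulated figures are the ones just defined on live births, and the overall proportion with its interval stays diluted either way. It can also be said that the endpoint is secondary and descriptive, with no formal comparison against the unexposed group. That limits the consequence but does not correct the estimate.

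A reader might infer four stronger points, which the protocol does not support.

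- *Every lost infant counts as infection-free.* No. Table 1 and Section 4.6.3.2 collect infections at pregnancy outcome, Table 1 also lists targeted follow-up, and late data are accepted until the registry closes. An infant infected and reported before being lost still counts as an event.
- *The bias is 20-25%.* No. That range was used to arrive at the live-birth estimates and says nothing about loss after birth.
- *Repeat infections in one infant are counted twice.* The wording leaves open whether infants or events are counted. Double counting is one reading, and the Reporting and Analysis Plan, which is not available here, may settle it.
- *Kaplan-Meier estimates at 3 and 6 months are ready to run.* Section 4.6.4 lists the assessment date and infection history since the last contact, but no onset date.

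**Conclusion.** The concern holds for the overall first-year proportion. The denominator is stated in the protocol, so this is not a detail left to the analysis plan, and it treats unknown infection status as no infection. The direction is certain for any loss that leaves infections unrecorded.

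The size cannot be taken from the document. Under the assumptions above it runs from about half a percentage point at 5% infant loss (9.4% against 9.9%) to two points at 20% (8.0% against 10.0%). It is smaller if infections are recorded before loss. The statement that relative understatement equals the share lost needs both equal risk in lost and followed infants and no early capture. The point should be corrected, but it touches one secondary endpoint and does not affect the birth-defect analysis.

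**What to change.** Amend Section 4.8.4.3 so that:

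- the main proportion is the number of infants with at least one qualifying infection, divided by the number of infants with pediatric follow-up from a health care provider covering the relevant Section 4.3.3 window (3, 6 or 12 months), with numerator and denominator drawn from the same infants;
- an infant who dies inside a window has known status and stays in;
- the live-birth proportion is kept, including infections recorded before loss, and labelled as a lower bound;
- the number of live-born infants without complete follow-up is shown beside each figure.

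Align Section 4.6.8.3 by saying how lost and partly followed infants enter these denominators. Use person-time or Kaplan-Meier estimates, censored at the last pediatric contact, only if infection onset dates are captured.

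The cost is a protocol wording change, one additional table and a slightly wider interval. The followed-infant proportion still assumes that lost infants resemble those followed, and should carry that caveat.
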